4.3. Exclusion Criteria (Parts A and B)

Subjects who meet *any* of the following exclusion criteria are not to be enrolled in this study.

- 1) Anticipated to start HIV-1 therapy between Days 1 and 9
- 2) Participation in any other clinical trial, including observational studies, without prior approval from the sponsor is prohibited while participating in this trial
- 3) Recent use of any approved or investigational antiretroviral drugs within 12 weeks prior to screening
- 4) Have taken any prescription medications or over-the-counter medications, including herbal products, within 42 days prior to start of study drug dosing without prior approval from the sponsor, with the exception of vitamins and/or acetaminophen and/or hormonal contraceptive medications
- 5) Known hypersensitivity to the study drug, the metabolites or formulation excipients, or to B/F/TAF
- 6) A new AIDS-defining condition diagnosed within the 30 days prior to screening (refer to [Appendix 5](#))
- 7) Hepatitis C virus (HCV) antibody positive and HCV RNA detectable
- 8) Chronic Hepatitis B Virus (HBV) infection, as determined by either:
 - Positive HBV surface antigen and negative HBV surface antibody, regardless of HBV core antibody status, at the screening visit
 - Positive HBV core antibody and negative HBV surface antibody, regardless of HBV surface antigen status, at the screening visit.
- 9) Pregnant or lactating females
- 10) Have an implanted defibrillator or pacemaker
- 11) Current alcohol or substance use judged by the Investigator to potentially interfere with subject study compliance
- 12) A history of malignancy within the past 5 years (prior to screening) or ongoing malignancy other than cutaneous Kaposi's sarcoma (KS), basal cell carcinoma, or resected, non-invasive cutaneous squamous carcinoma. Subjects with cutaneous KS are eligible, but must not have received any systemic therapy for KS within 42 days of Day 1 and must not be anticipated to require systemic therapy during the study
- 13) Active, serious infections (other than HIV-1 infection) requiring parenteral antibiotic or antifungal therapy within 42 days prior to Day 1

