$$\text{Female: } \frac{(140 - \text{age in years}) \times (\text{wt in kg}) \times 0.85}{72 \times (\text{serum creatinine in mg/dL})} = \text{CLcr (mL/min)}$$

13) Hepatic transaminases (AST and ALT) $\leq 5 \times$ upper limit of normal (ULN)

14) Alkaline phosphatase \leq ULN

15) Total bilirubin ≤ 1.5 mg/dL, or normal direct bilirubin

16) Adequate hematologic function (absolute neutrophil count $\geq 750/\text{mm}^3$; platelets $\geq 50,000/\text{mm}^3$; hemoglobin ≥ 8.5 g/dL) (Those with chronic neutropenia with no clinical significance can enroll at the discretion of the investigator.)

17) Females of childbearing potential (as defined in [Appendix 6](#) for Cohorts 1 - 5, and [Appendix 7](#) for Cohorts 6 - 8) must have a negative serum pregnancy test at screening.

18) Male and female subjects of childbearing potential who engage in heterosexual intercourse must agree to utilize protocol specified method(s) of contraception as described in [Appendix 6](#) for Cohorts 1 - 5, and [Appendix 7](#) for Cohorts 6 - 8.

19) Female subjects must refrain from egg donation and in vitro fertilization during treatment and until at least:

- 300 days following the dose of study drug, for Cohorts 1 – 5
- 7 days following the last dose of Biktarvy on the study, for Cohorts 6 – 8

20) **Cohorts 1 - 5:** Male subjects must refrain from sperm donation during treatment and until at least 360 days following the dose of study drug.

Cohorts 6 - 8: Male subjects must refrain from sperm donation during treatment on the study.

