6.6.1. Blood Samples

- Blood sample collection for the following laboratory analyses will be performed at every visit, unless specified:
 - Serum pregnancy test (females of childbearing potential only). If the test is positive, the subject will not be randomized (**Screening and Days 29, 57, 85, 113, 141, 169, 197 and 225**)
 - Serum FSH test (required for female subjects who have stopped menstruating for ≥ 12 months but do not have documentation of ovarian hormonal failure) (**Screening only**)
 - Urine pregnancy test (females of childbearing potential only). If the test is positive, confirmatory serum test should be sent and study drug dosing should be delayed until results obtained (**Day 1**)
 - Chemistry profile: alkaline phosphatase, AST, ALT, GGT, total bilirubin, direct and indirect bilirubin, total protein, albumin, LDH, CPK, bicarbonate, BUN, calcium, chloride, creatinine, glucose, phosphorus, magnesium, potassium, sodium, uric acid, amylase (reflex lipase testing is performed in subjects with total amylase $> 1.5 \times \text{ULN}$) (**All visits except Days 2, 4, 8 and 9**). Subjects will be required to fast overnight (≥ 6 hours) prior to visit on Days 3, 7, 10, 85, 169 and 225.
 - Estimated glomerular filtration rate according to the Cockcroft-Gault formula for Creatinine clearance (**All visits except Days 2, 4, 8 and 9**)
Male:
$$\frac{(140 - \text{age in years}) \times (\text{wt in kg})}{72 \times (\text{serum creatinine in mg/dL})} = \text{CLcr (mL/min)}$$

Female:
$$\frac{(140 - \text{age in years}) \times (\text{wt in kg}) \times 0.85}{72 \times (\text{serum creatinine in mg/dL})} = \text{CLcr (mL/min)}$$
 - Hematology profile: complete blood count (CBC) with differential and platelet count (**All visits except Days 2, 4, 8 and 9**)
 - CD4+ cell count (**Screening and Days 1, 10, 29, 43, 57, 85, 113, 141, 169, 197 and 225**)
 - Plasma HIV-1 RNA. Any subsequent HIV-1 genotype and phenotype testing will be performed as described in Section 6.7.
 - HIV-1 genotype and phenotype for PR, RT, IN, and capsid (**Screening only**)
 - HIV-1 capsid genotype and phenotype (**Day 10**)
 - HIV DNA genotyping (**Days 85, 169 and 225**)

- Hepatitis B virus (HBV) serologies (HBV surface antigen, HBV core antibody, HBV surface antibody) (**Screening only**)
- Hepatitis C virus (HCVAb) serology (**Screening only**)

CCU [REDACTED]

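### Exclusion 8 is headed chronic HBV infection, but both of its serology rules need a negative surface antibody, so candidates positive for surface antigen and surface antibody meet neither.

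*Protocol*

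**What the plan says.** Protocol Section 4.3 opens by making each exclusion sufficient on its own: "Subjects who meet *any* of the following exclusion criteria are not to be enrolled in this study". Exclusion 8 is introduced as "Chronic Hepatitis B Virus (HBV) infection, as determined by either" of two bullets, which work as its definition:

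- First bullet: "Positive HBV surface antigen and negative HBV surface antibody, regardless of HBV core antibody status, at the screening visit".
- Second bullet: "Positive HBV core antibody and negative HBV surface antibody, regardless of HBV surface antigen status, at the screening visit".

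Protocol Section 6.6.1 lists the markers these bullets need, at screening only: "Hepatitis B virus (HBV) serologies (HBV surface antigen, HBV core antibody, HBV surface antibody". The procedures table in Protocol Appendix 2 likewise shows HBV testing at screening and at no later visit. The key eligibility list in SAP Section 1.2 does not mention HBV.

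**The concern.** The heading names a condition, and the two bullets decide who has it. Because both bullets share one requirement, a negative surface antibody, a positive surface antibody switches off the whole criterion, even when surface antigen has been detected. Meanwhile the second bullet turns away a candidate who has core antibody but no antigen. Neither document explains why antigen status should stop mattering once surface antibody is present.

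What is at stake is the interpretation of liver findings. Every participant is to start B/F/TAF on Day 10 and continue to Day 225, and Part B also gives a single dose of TAF. AST, ALT and total bilirubin are among the graded laboratory tests listed in SAP Appendix 3. Groups are very small, so a single participant whose hepatitis B status is unclear carries visible weight in a group's liver-safety summary.

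**Working it through.** No sample size, power or error rate is involved, and the plan gives no figure to reproduce. The check is a truth table over the three screening markers.

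**Rule, from exclusion 8.** Excluded = (antigen positive AND surface antibody negative) OR (core antibody positive AND surface antibody negative).

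| Surface antigen | Surface antibody | Core antibody | First bullet | Second bullet | Result |
|---|---|---|---|---|---|
| + | + | + | no | no | not excluded |
| + | + | − | no | no | not excluded |
| + | − | + | yes | yes | excluded |
| + | − | − | yes | no | excluded |
| − | + | + | no | no | not excluded |
| − | + | − | no | no | not excluded |
| − | − | + | no | yes | excluded |
| − | − | − | no | no | not excluded |

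Three of 8 patterns are excluded. All four patterns with surface antibody present pass, and two of those are antigen positive. So 2 of the 4 antigen-positive patterns pass. The second bullet's indifference to antigen status does not help, because it too needs surface antibody to be negative.

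**Does anything else catch these two patterns?**

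- Inclusion 13 allows AST and ALT up to 5 × ULN. Inclusions 14 and 15 cap alkaline phosphatase at ULN and total bilirubin at 1.5 mg/dL (or require normal direct bilirubin). These limit overt liver disease but do not test HBV status.
- Exclusion 7 concerns hepatitis C only.
- Exclusion 13 is confined to "Active, serious infections (other than HIV-1 infection) requiring parenteral antibiotic or antifungal therapy within 42 days prior to Day 1".
- Exclusion 11 relies on investigator judgement, but only about alcohol or substance use. There is no general discretionary exclusion.
- No visible criterion uses HBV DNA. The visible list in Section 6.6.1 should not be taken as complete: an item after the hepatitis serologies is blacked out, and the list does not show the HCV RNA that exclusion 7 needs.

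**Weight of one participant**, from the planned group sizes in Protocol Sections 3.3 and 8.8:

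- GS-6207 arm, n = 6: 1/6 = 16.7%
- TAF cohort, n = 8: 1/8 = 12.5%
- Pooled placebo, 5 cohorts × 2 = 10: 1/10 = 10%

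**Effect of one possible edit.** If the first bullet dropped its surface-antibody condition, it would cover all 4 antigen-positive patterns. The second bullet would add the pattern with core antibody alone. That makes 4 + 1 = 5 of 8 excluded, with no antigen-positive pattern passing.

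**The case against.** The strongest reply is that exclusion 8 is an operational definition, applied consistently. It gives an answer for every combination of markers and always treats a positive surface antibody as eligible. Nothing in the documents says that the double-positive pattern is chronic infection, so the wording may be deliberate. This stands in part: intent cannot be settled from the text, and a reader who infers a proven drafting error goes too far. It does not remove the point, because a rule under this heading that passes detected antigen needs either a change or a stated reason.

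A second reply is that an investigator could exclude such a candidate on the heading alone. This is weak, since the heading hands the determination to the two bullets.

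Two stronger readings are tempting, and the documents support neither:

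- A reader might infer that starting or stopping B/F/TAF would change hepatitis B activity in such a participant and cause liver events. The documents do not say so. Protocol Section 1.5.2 reports only a favorable safety profile for TAF 25 mg in chronic hepatitis B. Section 5.5 covers Part A participants who have already stopped B/F/TAF, and says only which regimens they may not switch to.
- A reader might infer that the between-arm safety comparison would be confounded. SAP Sections 7.1.6.1 and 7.2.2.2 provide separate summaries of adverse events and graded laboratory abnormalities up to Day 10, so the Part A monotherapy period is largely insulated from anything linked to B/F/TAF. Part B has no control arm, and SAP Section 3 summarizes the two parts separately. SAP Section 7.2 plans no formal testing of laboratory data.

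**Conclusion.** The gap in the rule is real and follows from the wording alone: 2 of the 4 antigen-positive patterns meet neither bullet, and no other visible criterion or test excludes them. The practical consequence is small. The documents give no frequency for the pattern, so the number affected cannot be estimated from them. My assumption is that fewer than one participant would be expected. SAP Section 1.2 says Cohort 8 did not enroll, so at 8 per cohort the planned maximum is 7 × 8 = 56 rather than the approximately 64 in the protocol.

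If one such participant were enrolled, that person would make up 10% to 16.7% of a group and could blur the attribution of liver findings in the summaries that run throughout the study. It is a worthwhile low-cost correction, not a threat to the primary efficacy analysis. The conclusion rests on two things: the two bullets being the full definition of exclusion 8, and no blacked-out text supplying a further HBV criterion.

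**What to change.** Reconcile the heading of exclusion 8 with its two bullets. There are two ways to do it, and the sponsor must say which matches the intent:

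- Word the bullets so that surface-antigen-positive candidates are handled the same way whatever their surface antibody. One example is to remove the surface-antibody condition from the first bullet and leave the second unchanged.
- Keep the bullets, state that admitting candidates positive for both markers is intended, and give the reason.

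The cost is a few words in one criterion. All three markers are already measured at screening, so no test or visit is added, and little effect on recruitment is expected. The same screening results would show whether anyone with this pattern was enrolled, which would replace the assumption about numbers with a count.

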5. INVESTIGATIONAL MEDICINAL PRODUCT AND B/F/TAF

5.1. Randomization, Blinding and Treatment Codes

Part A

Subjects will be assigned a screening number at the time of consent. It is the responsibility of the investigator to ensure that the subject is eligible for the study prior to enrollment.

Following completion of screening procedures, eligible subjects will be randomized in a 3:1 ratio within each cohort to receive either GS-6207 (n=6) or placebo (n=2) on Day 1, and assigned a subject number.

All screening tests and procedures must be completed and reviewed by the investigator prior to the administration of the study drug on Day 1. Once a subject number has been assigned to a subject, it will not be reassigned to another subject. If necessary, replacement subjects may be enrolled after discussion and approval from Sponsor. A new unique subject number will be assigned to the replacement subject.

The study pharmacist, or designee will remain unblinded throughout the study to prepare the study drug. The designated site staff administering the study drug will also remain unblinded. For additional information on maintaining the study blind, please refer to the study Pharmacy Manual. The Pharmacokinetics File Administrator, or designee, who facilitates data transfer of PK files between Gilead and vendors, will remain unblinded.

Part B

Subjects will be assigned a screening number at the time of consent. It is the responsibility of the investigator to ensure that the subject is eligible for the study prior to enrollment.

Following completion of screening procedures, eligible subjects will be enrolled to receive TAF and will be assigned a subject number.

All screening tests and procedures must be completed and reviewed by the investigator prior to the administration of the study drug on Day 1. Once a subject number has been assigned to a subject, it will not be reassigned to another subject. If necessary, replacement subjects may be enrolled after discussion and approval from Sponsor. A new unique subject number will be assigned to the replacement subject.

5.1.1. Procedures for Breaking Treatment Codes (Part A)

In the event of a medical emergency where breaking the blind is required to provide medical care to the subject, the investigator may obtain treatment assignment directly from the IWRS system for that subject. Gilead recommends but does not require that the investigator contact the Gilead medical monitor before breaking the blind. Treatment assignment should remain blinded unless

that knowledge is necessary to determine subject emergency medical care. The rationale for unblinding must be clearly explained in source documentation and on the case report form/electronic case report form (eCRF), along with the date on which the treatment assignment was obtained. The investigator is requested to contact the Gilead medical monitor promptly in case of any treatment unblinding.

All subjects will be followed until study completion unless consent to do so is specifically withdrawn by the subject.

Gilead Pharmacovigilance and Epidemiology (PVE) may independently unblind cases for expedited reporting of suspected unexpected serious adverse reactions (SUSARs).

5.2. Description and Handling GS-6207, TAF and B/F/TAF

5.2.1. Formulation

5.2.1.1. GS-6207 and Placebo

GS-6207 injectable suspension, 100 mg/mL is a sterile, preservative-free, white to off-white to tan suspension for subcutaneous injection. In addition to the active ingredient, the suspension contains the following inactive ingredients: poloxamer 188, sodium chloride, phosphate buffer, and water for injection.

The placebo is a sterile, clear, colorless solution for subcutaneous injection. The solution contains the following inactive ingredients: poloxamer 188, sodium chloride, phosphate buffer, and water for injection.

5.2.1.2. TAF

TAF tablets, 25 mg, are yellow, round, film-coated tablets debossed with "GSI" on one side of the tablet and "25" on the other side of the tablet. In addition to the active ingredient, the tablets contain the following inactive ingredients: lactose monohydrate, microcrystalline cellulose, croscarmellose sodium, magnesium stearate, polyvinyl alcohol, titanium dioxide, polyethylene glycol, talc, and iron oxide yellow.

5.2.1.3. Bictegravir/Emtricitabine/Tenofovir Alafenamide (B/F/TAF, 50/200/25 mg)

Bictegravir /Emtricitabine /Tenofovir Alafenamide (B/F/TAF, 50/200/25 mg) tablets are capsule-shaped, film-coated purplish-brown, debossed with "GSI" on one side of the tablet and "9883" on the other side of the tablet. Each tablet core contains 50 mg of bictegravir, 200 mg of emtricitabine, and 25 mg of tenofovir alafenamide. In addition to the active ingredients, the B/F/TAF tablets contain croscarmellose sodium, magnesium stearate, and microcrystalline cellulose. The tablet cores are film-coated with iron oxide red, iron oxide black, polyethylene glycol, polyvinyl alcohol, talc, and titanium dioxide.

5.2.2. Packaging and Labeling

5.2.2.1. GS-6207 and Placebo

GS-6207 injectable suspension, 100 mg/mL, and placebo solution are each filled into a 3 mL borosilicate glass vial and closed with a rubber stopper and aluminum seal with a polypropylene flip-off cap. Each single use vial contains sufficient volume (1.2 mL) to allow withdrawal of 1 mL of GS-6207 injectable suspension or placebo solution.

The vials are labeled and placed into secondary packaging for storage.

Study drug to be distributed to centers in the US shall be labeled to meet requirements of the US Food and Drug Administration (FDA) and/or other local regulations as applicable.

5.2.2.2. TAF

TAF tablets are packaged in white, high density polyethylene (HDPE) bottles. Each bottle contains 30 tablets and a silica gel desiccant and polyester packing material. Each bottle is enclosed with a white, continuous thread, child-resistant polypropylene screw cap with an induction-sealed and aluminum-faced liner.

Study drug to be distributed to centers in the US shall be labeled to meet requirements of the US Food and Drug Administration (FDA) and/or other local regulations as applicable.

5.2.2.3. Bictegravir/Emtricitabine/Tenofovir Alafenamide (B/F/TAF, 50/200/25 mg)

Bictegravir /Emtricitabine /Tenofovir Alafenamide (B/F/TAF, 50/200/25 mg) is packaged in white, high density polyethylene (HDPE) bottles. Each bottle contains 30 tablets, silica gel desiccant and polyester packing material. Each bottle is enclosed with a white, continuous thread, child-resistant polypropylene screw cap with an induction-sealed and aluminum-faced liner.

B/F/TAF to be distributed to centers in the US shall be labeled to meet requirements of the US Food and Drug Administration (FDA) and/or other local regulations as applicable.

5.2.3. Storage and Handling

5.2.3.1. GS-6207 and Placebo

GS-6207 100 mg/mL injectable suspension and placebo solution vials should be stored refrigerated at 2 °C to 8 °C (36 °F to 46 °F). Storage conditions are specified on the label. Until dispensed for dosing, all vials of study drugs should be stored in a securely locked area, accessible only to authorized site personnel.

To ensure the sterility, stability, and proper identification, study drug(s) should not be stored in a container other than the container in which they were supplied.

Measures that minimize drug contact with the body should always be considered during handling, preparation, and disposal procedures.

5.2.3.2. TAF

TAF tablets should be stored at controlled room temperature of 25°C (77°F); excursions are permitted between 15°C and 30°C (59°F and 86°F). Storage conditions are specified on the label.

Until dispensed to the subjects, all bottles of study drugs should be stored in a securely locked area, accessible only to authorized site personnel. Measures that minimize drug contact with the body should always be considered during handling, preparation, and disposal procedures.

5.2.3.3. Bictegravir/Emtricitabine/Tenofovir Alafenamide (B/F/TAF, 50/200/25 mg)

Bictegravir /Emtricitabine /Tenofovir Alafenamide (B/F/TAF, 50/200/25 mg) stored at controlled room temperature of 25°C (77°F); excursions are permitted between 15°C and 30°C (59°F and 86°F). Storage conditions are specified on the label. Until dispensed to the subjects, all bottles of B/F/TAF should be stored in a securely locked area, accessible only to authorized site personnel.

To ensure the stability and proper identification, B/F/TAF should not be stored in a container other than the container in which they were supplied. Keep the bottle tightly closed to protect from moisture.

Measures that minimize drug contact with the body should always be considered during handling, preparation, and disposal procedures.

5.3. Dosage and Administration of GS-6207 (Part A, Cohorts 1 - 5)

Part A of this study may enroll up to 5 cohorts of approximately 8 unique subjects per cohort. All subjects will be enrolled after the completion of screening procedures and following confirmation of study eligibility. Within each Cohort (n=8) in Part A, subjects will be randomized in a 3:1 ratio to receive active GS-6207 (n=6) or placebo (n=2).

A single dose of GS-6207 or placebo will be administered subcutaneously (SC) in the abdomen on Day 1. GS-6207 doses may be administered as multiple SC injections at different abdominal sites, as appropriate. In the case where multiple injections are administered for a given dose, the first and last injections should be no more than 30 minutes apart. If necessary for practical reasons, the period may be extended up to 45 minutes.

Cohort	Treatment
1	150 mg GS-6207 or placebo
2	50 mg GS-6207 or placebo
3	450 mg GS-6207 or placebo
4	20 mg GS-6207 or placebo
5	750 mg GS-6207 or placebo

The Sponsor may elect to hold dosing, or stop study enrollment at any time based on review of preliminary safety data.

The doses to be evaluated in Cohorts 2 through 5 will be determined based on cumulative safety (through at least Day 14), available PK and viral kinetic data from previous cohorts as well as available safety (through at least Day 14) and pharmacokinetic data from Study GS-US-200-4070 (Phase 1, first-in-human, single ascending dose study of GS-6207 SC suspension formulation). Cohorts 2-5 may be initiated in parallel. Selected doses will be either lower than, or no more than 3-fold higher than, previously evaluated doses either in this study or in Study GS-US-200-4070; the same SC suspension formulation is being administered in both studies. The highest proposed dose in this study, GS-6207 900 mg, represents a 2-fold dose escalation over GS-6207 450 mg, which has been shown to be safe and well tolerated in Study GS-US-200-4070, based on a blinded review of safety data.

